## **15.5 Investigator Reporting Responsibilities to the Sponsor**

### **15.5.1 Adverse Events**

Line listings, frequency tables and other summary AE data will be submitted to the IND sponsor when requested for periodic safety assessments, review of IND Annual Reports, review of IND Safety Reports, and preparation of final study reports.

### **15.5.2 Serious Adverse Events**

All SAEs (regardless of relationship and whether or not they are also UPs) must be reported on the SERF and sent to the CSO by fax or email attachment. Deaths and immediately life-threatening SAEs must be reported to the CSO within 1 business day after the site becomes aware of the event. All other SAEs must be reported within 3 business days of site awareness.

**15.5.3 Unanticipated Problems**

UPs that are also AEs must be reported to the CSO by fax or e-mail attachment using the NIH Reportable Events Form no later than 7 calendar days of site awareness of the event. UPs that are not AEs are not reported to the CSO.

**15.5.4 Pregnancy**

Pregnancy itself is not an AE. However, complications of pregnancies are AEs and may be SAEs. Pertinent obstetrical information for all pregnancies will be reported to the CSO and LMIV via fax or email within 3 business days from the site awareness of the pregnancy. All pregnancies will be reported on the Pregnancy Notification/Outcome Form to the CSO within 1 business day from site awareness.

Pregnancy outcome data (e.g., delivery outcome, spontaneous or elective termination of the pregnancy) will be reported to the CSO and LMIV within 3 business days of the site's awareness.

In the event of pregnancy, the following steps will be taken:

- Discontinue the study agent.
- Discuss with women who become pregnant continued participation in the study, including continued safety/research labs (at investigator's discretion given blood volumes), direct skin feeds, and clinical visits.
- Report to FMPOS EC as an informational item.
- Report to the DSMB, Sponsor Medical Monitor, and Malian Independent Safety Monitor (ISM).
- Advise research participant to notify the obstetrician of study participation and potential study agent exposure.

## 15.6 Investigator Reporting Procedures to the NIH IRB

### 15.6.1 Definitions

**Protocol Deviation:** Any change, divergence, or departure from the IRB-approved research protocol.

**Major Deviations:** Deviations from the IRB approved protocol that have, or may have the potential to, negatively impact, the rights, welfare or safety of the subject, or to substantially negatively impact the scientific integrity or validity of the study.

**Minor Deviations:** Deviations that do not have the potential to negatively impact the rights, safety, or welfare of subjects or others, or the scientific integrity or validity of the study.

**Non-Compliance:** Failure of investigator(s) to follow the applicable laws, regulations, or institutional policies governing the protection of human subjects in research, or the requirements or determinations of the IRB, whether intentional or not. Failure of subjects to comply with the research protocol does not represent non-compliance unless that failure is due to an action or omission of a member of the research team, for example, the failure to give adequate instruction to the subject.

**Serious non-compliance:** Non-compliance, whether intentional or not, that results in harm or otherwise materially compromises the rights, welfare and/or safety of the subject. Non-compliance that materially effects the scientific integrity or validity of the research may be considered serious non-compliance, even if it does not result in direct harm to research subjects.

**Continuing non-compliance:** A pattern of recurring non-compliance that either has resulted, or, if continued, may result in harm to subjects or otherwise materially compromise the rights, welfare and/or safety of subjects, affect the scientific integrity of the study or validity of the results. The pattern may comprise repetition of the same non-compliant action(s), or different noncompliant events. Such non-compliance may be unintentional (e.g. due to lack of understanding, knowledge, or commitment), or intentional (e.g. due to deliberate choice to ignore or compromise the requirements of any applicable regulation, organizational policy, or determination of the IRB).

#### 15.6.1.1 Expedited Reporting to the NIH IRB and FMPOS EC

**Non-compliance:** Any actual or suspected non-compliance by any investigator or entity associated with the protocol must be reported by the NIH PI/designee within 7 calendar days of any investigator or individual associated with the protocol first becoming aware, unless otherwise indicated in this policy.

Non-NIH IRB determinations of serious and/or continuing noncompliance about an NIH investigator: If the NIH is relying on a non-NIH IRB and the Reviewing IRB makes a determination of serious and/or continuing non-compliance regarding an NIH investigator, then, even if the determination has already been provided to OHSRP either directly or via the NIH Institutional Official (IO)/designee, the NIH PI/designee must report this in iRIS within 7 calendar days of any member of the research team being notified of the determination by the Reviewing IRB. The NIH PI must provide the OHSRP office of Compliance and Training with documentation from the Reviewing IRB unless this documentation has already been provided directly to the office by the Reviewing IRB or via the IO.

**Major Deviation:** A deviation must be reported within 7 calendar days of an investigator becoming aware of an actual or suspected deviation. Although protocol deviations are also non-compliance, these should only be reported once as deviations.

**Unanticipated Problem (UP):** A UP must be reported within 7 calendar days of an investigator becoming aware of the actual or suspected UP.

**Death:** Any death of a research subject that is possibly, probably or definitely related to the research must be reported within 24 hours of an investigator becoming aware of the death.

New information that might affect the willingness of a subject to enroll or remain in the study should be reported within 7 calendar days of an investigator first becoming aware.

Any suspension or termination of research activities, including holds on new enrollment, placed upon the research by the study sponsor, NIH or IC leadership, or any regulatory agency must be reported within 7 calendar days of an investigator becoming aware.

Investigators must provide the following information to the IRB in summary format at the time of continuing review: Minor protocol deviations; Adverse events and Serious Adverse Events that do not meet the definition of an UP.

Investigators are required to immediately (i.e., no longer than 10 days) report SAEs or UADEs to the study sponsor and, if also an actual or suspected UP, to the IRB within 7 calendar days of an investigator becoming aware.

#### **15.6.1.2 Annual Reporting to the NIH IRB and FMPOS EC**

All events will be reported to the NIH IRB and FMPOS EC in summary format at the time of Continuing Review according to NIH policy 801.

## 15.7 Investigator Reporting Responsibilities to the Local IRB

Investigators are responsible for submitting IND Safety Reports and UP summaries that are received from the IND sponsor to the FMPOS EC. Investigators must also comply with all FMPOS EC reporting requirements, including expedited and annual reporting requirements.

## 15.8 Sponsor's Reporting Responsibilities

SUSARs, as defined in Title 21 of the United States Code of Federal Regulations (CFR) Part 312.32 and determined by the IND sponsor, will be reported to FDA and all participating investigators as IND Safety Reports.

The IND sponsor will also submit an IND Annual Report of the progress of the investigation to the FDA as defined in 21 CFR 312.33.

## 15.9 Pausing Rules for the Protocol

Pausing is the suspension of administration of study agent to a single subject or specified group until a decision is made whether or not to resume administration of the study agent.

### 15.9.1 Pausing Rules for an Individual Subject

The pausing criteria for a SINGLE subject in this study include any of the following; note Year 1 and Year 2 will be evaluated independently given time between dosing:

- A subject experiences one SAE that is determined as possibly, probably, or definitely related to a study agent
- A subject experiences  $\geq 2$  Grade 3 or greater AEs that are deemed not to be a SAE (solicited local/systemic or unsolicited; lasting 48 hours or more) that are possibly, probably, or definitely related to a study agent, within the 7 days post vaccination
- A subject experiences  $\geq 2$  Grade 2 or greater laboratory abnormality (see [Appendix C](#)) or any Grade 3 or higher laboratory abnormality that are not deemed to be a SAE and are possibly, probably, or definitely related to the study agent, within the 7 days post vaccination
- $\geq 1$  subject experiences any local or solicited AE leading to hospitalization, or fever  $>40^{\circ}\text{C}$  ( $104^{\circ}\text{F}$ ) that is possibly, probably, or definitely related to the vaccine, or necrosis at the injection site, within the 7 days post vaccination
- Any safety issue that the site investigator determines should pause administration of a study agent to a single subject.

The CSO, in collaboration with the PI, may also pause for an individual subject if a safety concern is identified during routine aggregate data analysis.

### 15.9.2 Pausing Rules for a Particular Age Group

The pausing criteria for a SPECIFIC AGE group in this study include any of the following; note Year 1 and Year 2 will be evaluated independently given time between dosing:

- An age group enrolled (e.g. 5-8 years of age, 9-18 years of age) experiences one SAE that is determined as possibly, probably, or definitely related to a study agent
- $\geq 5\%$  of a specific age group experiences Grade 3 or greater AEs (solicited local/systemic or unsolicited; lasting 48 hours or more) that are possibly, probably, or definitely related to a study agent, within the 7 days post vaccination
- $\geq 10\%$  of a specific age group experiences Grade 2 or greater laboratory abnormality (see [Appendix C](#)) or  $\geq 5\%$  Grade 3 or higher laboratory abnormality that are possibly, probably, or definitely related to the study agent, within the 7 days post vaccination
- Any safety issue or identifiable trend in AE reporting that the site investigator determines should pause administration of a study agent to a specific age group

The CSO, in collaboration with the PI, may also pause a specific age group if a safety concern is identified during routine aggregate data analysis.

### 15.9.3 Reporting a Pause

If a pausing criterion is met, a description of the AE(s) or safety issue must be reported by the PI within 2 business days to the CSO, the IRB/EC, and the DSMB by fax or email.

### 15.9.4 Resumption of a Paused Study

The CSO, in collaboration with the PI and DSMB, will determine whether or not it is safe to resume administration of the study agent to the subject or a specific age group. The PI will notify the IRB/EC of the decision on resumption of the study agent. A subject who does not resume to receive the study agent will continue to be followed for safety.

## 15.10 Halting Rules for the Protocol

Halting the study requires immediate discontinuation of study agent administered for all subjects and suspension of enrollment until a decision is made whether or not to continue enrollment and study agent administration.

The following criteria will be used to define unacceptable reactogenicity of the malaria vaccine (AEs that are possibly, probably, or definitely related to the vaccine will be considered “related” and will be summarized as such); note Year 1 and Year 2 will be evaluated independently given time between dosing:

- One or more subjects experience death or any life-threatening SAE, **or**

- $\geq 2$  subjects experience an SAE as defined in **Section 15.1** of this protocol that is determined to be possibly, probably, or definitely related to the vaccine, **or**
- $\geq 1$  subjects are withdrawn from the study (by investigator or subject request) following a Grade 3 AE that is determined to be possibly, probably, or definitely related to the vaccine, **or**
- $\geq 1$  subjects experience a hypersensitivity reaction (e.g. anaphylaxis, diffuse urticaria) that is determined to be possibly, probably, or definitely related to the vaccine, **or**
- $\geq 1$  subjects experience any local or solicited AE leading to hospitalization, or fever  $>40^{\circ}\text{C}$  ( $104^{\circ}\text{F}$ ) that is possibly, probably, or definitely related to the vaccine, or necrosis at the injection site, within the 7 days post vaccination, **or**
- $\geq 10\%$  subjects enrolled experience any Grade 3 solicited local AE (lasting 48 hours or more) that is determined to be possibly, probably, or definitely related to the vaccine as defined in this protocol, within the 7 days post vaccination, **or**
- $\geq 10\%$  subjects enrolled experience any Grade 3 solicited systemic AE (lasting 48 hours or more) that is determined to be possibly, probably, or definitely related to the vaccine as defined in this protocol, within the 7 days post vaccination, **or**
- $\geq 30\%$  subjects enrolled experience the same Grade 2 or higher laboratory abnormality (see **Appendix C**) or  $\geq 10\%$  subjects enrolled experience the same Grade 3 or higher laboratory abnormality regardless of vaccine relationship, within the 7 days post vaccination, **or**
- $\geq 10\%$  subjects enrolled experience the same or similar Grade 3 unsolicited AE that is determined to be possibly, probably, or definitely related to the vaccine as defined in this protocol, **or**
- Any safety issue that the study PI or IND sponsor determines should halt the study.

The PI and/or CSO will determine if the study should be halted. In addition, the FDA may halt the study at any time following review of any safety concerns. The NIH IRB or FMPOS EC may also halt the study.

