### 3.3 Pfs230D1M-EPA/AS01 in Healthy Malian Children and Adults (19-I-N086)

The Phase 2 study of the safety, immunogenicity, vaccine activity, and vaccine efficacy of Pfs230D1M-EPA/AS01 against *Plasmodium falciparum* malaria in VUs in Doneguebougou, Mali and surrounding villages started the age de-escalation Pilot Phase in April 2019 (9-18 yo) and May 2019 (5-8 yo) followed by Main Phase enrollment and vaccinations in June 2019.

For the initial Pilot Phase safety arms, 30 subjects in each age group received Vaccinations #1, #2 on a 0, 28 day schedule and then were scheduled to receive Vaccination #3 along with the majority of their vaccine unit (VU) members, resulting in a final Vaccination schedule of 0, 28, 126 days. Main Phase subjects (vaccinees; Arms 3a-3f) started enrollment in June 2019 and completed enrollment in September 2019. Subjects in the Main Phase are scheduled to receive vaccinations on a 0, 28, 56 day schedule.

All study vaccinations for the primary series have been completed as of 30 November 2020. Vaccination #3 was completed in 97.9% of vaccinees (1078/1101) who received Vaccination #1 and 1066/1101 (97%) of participants had all three doses of the vaccine. Children aged 1-4 year old (Arm 4a/4b; n=192) enrolled with their VU prior to dose #3. Direct skin feeds started in 9-18 year old subjects (Arms 1a/1b/3c/3d) in Sep 2019 and ended in March 2020. Summary of study enrollment, vaccination, DSF progress is summarized below in [Table 7](#).

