#### 3.3.1.1 1-4 Years Old (Unvaccinated)

At the time of the fourth dose amendment (V5.0), 192 children 1-4 years of age had enrolled in the study. Children in this age group did not nor will not receive vaccinations but did receive AL treatment at enrollment and underwent regular blood draws during the study. Most commonly reported AE has been malaria and rhinitis. Grade 3 AEs have been reported in 14 kids (14/192, 7.3%) with the most commonly reported Grade 3 AE being malaria, as expected. One SAE (malaria) has been reported with associated anemia; unrelated to study participation.

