## 6.2.2 Secondary Objectives

- To assess vaccine efficacy of Pfs230D1M-EPA/AS01 against *P. falciparum* infection measured by blood smear (All Arms except Arms 3e/3f)
- To assess safety and reactogenicity of administration of Pfs230D1M-EPA/AS01 (All Arms except 4a/4b)
- To assess immunogenicity as measured by enzyme-linked immunosorbent assay (ELISA) titer response to Pfs230D1M (All Arms except Arms 4a/4b)
- To assess functional antibody response by standard membrane feeding assay (SMFA) to Pfs230D1M (All Arms except Arms 4a/4b)

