Vaccination #3 = study day 112/42 for Arms 2a/2b, 3a/3b; for Arms 4a/4b this is study day -14). Preteen and adolescent subjects in Arms 1a/1b, 3c/3d will also be assessed by DSF for vaccine activity starting 2 weeks post receipt of vaccination #3; DSFs will be completed every 2 weeks for a total of 8 DSFs.

All enrolled subjects (Groups 1-4, except adults on a less regular active follow-up) from the family compound will be monitored for patent parasitemia every 2 weeks, and during unscheduled visits if clinically indicated, for at least 6 months up to 12 months post vaccination, with time to patent parasitemia being evaluated as a vaccine efficacy timepoint in children 1-8 years of age as well as 9-18 years of age within the compounds (separate secondary evaluation given expected nighttime mobility and no pre-transmission season AL treatment).

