#### 8.4 Study Definitions

**Screened:** Subjects will receive a screening identification number (SC-XXX-XXX) when the informed consent is signed, and will either be determined as “enrolled” or “screen failures” as noted below; subjects within the same vaccine unit will be noted by the same first 3 numbers (SC-XXX-xxx) of their screening identification.

- Screening may be completed over the course of multiple visits.
- Screening will occur within 56 days prior to enrollment into the study.
- If the screening visit is >56 days prior to enrollment (determined by the date of each component), then an updated medical review, physical exam/vital signs, repeat Malaria Comprehension Exam, and repeat laboratory evaluation (inclusive of safety labs, human immunodeficiency virus [HIV], EKG) will be completed to determine eligibility for enrollment.

**Enrolled:** Subjects will be considered enrolled beginning with the receipt of the first blood draw and first AL dose.

- Final study number assigned – MV-19-XXX-XXX-X [MV-19-(vaccine unit #)-(study # per age)-(letter for QC)]
  - Given the last three numbers of the study number are dependent on age and requirement by the electronic database to have a study number during screening, if a child/young adult changes age categorization (4→5-year-old, 8→9-year-old, 18→19-year old) between screening and enrollment a new study ID will be assigned categorizing the study subject as above. The screening identification number will not change.

**Randomized:** Subjects are considered randomized when their family compound/vaccine unit undergoes randomization collectively at the time of first vaccination of their first family member. A compound/family may be randomized once the following criteria are met:

- Approximately 80% of the family compound/vaccine unit preliminarily eligible to be vaccinated has signed consent, agreed to participate in the study, and has been found preliminarily eligible for enrollment
- Entire family/compound will be randomized as a collective whole at the time of first vaccination in any family compound/vaccine unit participant
- To note: prior to the start of the study, the study geographers, based off GPS coordinates and village census assigned family compounds into vaccine units which were randomized as a unit.

**Re-enrolled:** Subjects are considered re-enrolled for Year 2 of follow-up when they complete the following:

- Re-consent

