- Successfully rescreen and meet inclusion/exclusion criteria for Year 2
- Receive either AL (1-8 years old only) and/or vaccine (scheduled dose #4)

**Screen Failures:** Subjects are considered screen failures when they meet 1 of the following criteria after signing consent:

- Screening results reveal that the subject is ineligible per **Section 11.1**
- Subject withdraws consent before being randomized.
- Family compound/Vaccine unit preliminary enrollment is significantly lower than approximately 80%, including low estimated pediatric participation.

**Discontinued:** Subjects are considered discontinued when they meet 1 or more of the following criteria:

- Subject withdraws consent after being vaccinated and/or randomized.
- Subject is withdrawn by the PI/sponsor after being vaccinated and/or randomized.

**Completed:** Subjects are considered completed when they complete the final study visit for their arm.

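### The percentage halting rules are a share of subjects enrolled, which by definition includes the 192 never-vaccinated Group 4 children; that loosens 10% and 30% to about 11.8% and 35.2% of vaccinees

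*Combined protocol and SAP*

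**What the plan says.** Section 15.10 lists criteria meant to define unacceptable reactogenicity of the malaria vaccine. Four bullets carry percentage thresholds, five in all:

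- 10% for Grade 3 solicited local events;
- 10% for Grade 3 solicited systemic events;
- 30% for the same Grade 2 or higher laboratory abnormality, and 10% for Grade 3 or higher, the latter worded "subjects enrolled experience the same Grade 3 or higher laboratory abnormality regardless of vaccine relationship";
- 10% for the same or similar related Grade 3 unsolicited event.

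Each is a share of the subjects enrolled, and Year 1 and Year 2 are evaluated separately. Under Section 15.10.1 a met rule must be reported within 1 business day.

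Enrolled is a defined term. Section 8.4 states: "Subjects will be considered enrolled beginning with the receipt of the first blood draw and first AL dose". For Year 2, after re-consent and re-screening, the last condition for re-enrolment is: "Receive either AL (1-8 years old only) and/or vaccine (scheduled dose #4".

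Other sections count Group 4 as enrolled. Section 7.2.2 has "All enrolled subjects (Groups 1-4, except adults on a less regular active follow-up", and Tables 7 and 12 both list 192 enrolled children aged 1-4. Section 3.3.1.1 says of them: "Children in this age group did not nor will not receive vaccinations". Section 6.2.2 leaves them out of the safety objective: "To assess safety and reactogenicity of administration of Pfs230D1M-EPA/AS01 (All Arms except 4a/4b".

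**The concern.** A Group 4 child has no post-vaccination window and cannot have a vaccine-related event. The Group 4 schedule in Appendix A contains malaria smear and PCR but no blood count, ALT or creatinine. These children therefore add to the denominator of every percentage halt and to the numerator of none.

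The defined term and the purpose of the section point in different directions. Two careful readers could compute different trigger counts from the same data, and the literal reading gives the later trigger. At stake is the point at which a halting rule counts as met and the report to the sponsor's safety office, the ethics bodies and the DSMB falls due.

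**Working it through.** **Inputs** (Table 7, checked against Section 3.3 and Table 12)

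- Received at least one vaccine: 30 + 30 + 183 + 368 + 490 = 1,101. This reproduces the 1,101 in Section 3.3.
- Enrolled in the vaccine arms: 30 + 30 + 185 + 369 + 495 = 1,109, which is 8 more than were dosed.
- Group 4 enrolled: 192.
- All enrolled: 1,109 + 192 = 1,301. Table 12 agrees: 192 + 215 + 399 + 495 = 1,301.

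**Trigger counts.** The trigger is the smallest whole number of subjects that reaches the percentage times the denominator. It is then expressed as a share of the 1,101 vaccinees.

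| Denominator | 10% rules | 30% rule |
|---|---|---|
| Vaccinees only, 1,101 | 110.1 → 111 (10.1%) | 330.3 → 331 (30.1%) |
| Vaccinees plus Group 4, 1,293 | 129.3 → 130 (11.8%) | 387.9 → 388 (35.2%) |
| All enrolled, 1,301 | 130.1 → 131 (11.9%) | 390.3 → 391 (35.5%) |
| Enrolled in vaccine arms, 1,109 | 110.9 → 111 (10.1%) | 332.7 → 333 (30.2%) |

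Against vaccinees only, Group 4 adds 130 − 111 = 19 affected subjects at 10% and 388 − 331 = 57 at 30%.

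**Timing.** Group 4 children "enrolled with their VU prior to dose #3", from August to November 2019 (Table 7). The dilution was absent at the first doses and reached these figures only when all 192 had joined.

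**Year 2.** Section 3.3 reports the primary series complete, so only dose 4 can be affected. Re-enrolled counts are not given. Assume between 80% and 100% retention in each group:

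- All vaccinees and 80% of Group 4 (154): 1,101 + 154 = 1,255. Triggers are 126 (126/1,101 = 11.4%) and 377 (34.2%).
- 80% of vaccinees (881) and all of Group 4: 881 + 192 = 1,073. Triggers are 108 (108/881 = 12.3%) and 322 (36.5%).

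**What acts earlier.** Section 15.9.2 pauses an age group when at least 5% "of a specific age group experiences Grade 3 or greater AEs" that are related, last 48 hours or more and fall within 7 days of vaccination. On Year 1 vaccinees that means 11 of 213 (ages 5-8), 20 of 398 (ages 9-18) and 25 of 490 (adults, if treated as an age group; the section names the two paediatric groups only as examples). At most 10 + 19 + 24 = 53 vaccinees could have such an event without a pause, well under 111. The laboratory pauses in Sections 15.9.1 and 15.9.2 require relatedness, so they do not cover the laboratory halt in the same way.

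**Observed events at the time of V5.0** (Sections 3.3.1.2 to 3.3.1.4). Vaccinees with any Grade 3 event of any cause: 16 + 23 + 11 = 50, and 50/1,101 = 4.5%. Related Grade 3 events: 4 + 3 + 1 = 8.

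**The case against.** The strongest reply is that nobody would read the rule this way. Section 15.10 is about reactogenicity of the vaccine. Three of its four percentage bullets are limited to 7 days after vaccination, and the fourth requires relatedness to the vaccine. The safety objective excludes Arms 4a/4b, and the neighbouring pausing rule illustrates an enrolled age group with vaccinated groups only. Nothing in the documents shows that the share was ever computed over 1,293 or 1,301. This is fair, and context does favour vaccinees. But the term is defined in the same document, and a halting threshold should yield one number.

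A second reply is that the consequence is close to nil. The age-group pause precedes both solicited-event halts. One study withdrawal after a related Grade 3 event is itself a halt. Section 15.12 stops further doses after most related Grade 3 events. The principal investigator reviews abnormal laboratory results routinely, and the investigator or sponsor may halt for any safety issue. Most of this stands and sets the severity. It does not supply an undiluted percentage rule for laboratory abnormalities judged unrelated. Unsolicited events later than 7 days are covered only in part, by Section 15.12 and by discretion.

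A third reply is that Section 15.10 says enrolled, not re-enrolled, so the Year 2 range is not the literal reading. That is correct. The literal denominator of 1,301 exceeds both 1,255 and 1,073, so the literal reading dilutes at least as much.

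**Conclusion.** The point holds and is minor. Read with its own definition, the denominator includes 192 children who cannot have a qualifying event, and they alone move the Year 1 thresholds from 10% and 30% to 11.8% and 35.2% of vaccinees. For dose 4, the only remaining dose, the range is 11.4% to 12.3% and 34.2% to 36.5% of recipients; this rests on the assumed 80% to 100% retention, because the documents give no Year 2 counts.

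The rule most exposed is the laboratory halt that applies whatever the judged relationship. No observed rate came near a trigger, and any halt remains a decision of the investigator or the sponsor's safety office. Pooling comparator recipients in the denominator is a separate matter and is not part of this point.

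**What to change.** In the four percentage bullets of Section 15.10, replace the words for the denominator with: *subjects enrolled (Year 2: re-enrolled) in the vaccinated arms, Arms 4a/4b excluded*. Keep the percentages. Comparator recipients stay in, because the trial is double-blind and they can have events. The denominator accrues as it does now, less Group 4, and does not become a running count per dose.

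The wording leaves in a few subjects without the relevant dose: the 8 undosed in Year 1, and any child aged 5-8 who re-enrols on AL alone. On Year 1 counts the effect of the 8 is negligible (10.1% and 30.2% of vaccinees). Writing *subjects vaccinated* would remove them too, with triggers of 111 and 331.

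The cost is one phrase and a slightly earlier halt: on Year 1 counts, 111 instead of 131 subjects at the 10% rules and 333 instead of 391 at the 30% rule.
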